2.2 Analysis sets

The following analysis sets will be used in this trial:

Randomized set: The randomized set will be defined as all patients, who were randomized.

Unless otherwise specified, mis-randomized patients (mis-randomized in IRT) will be excluded from the randomized set.

Mis-randomized patients are defined as those patients, who were mistakenly randomized into the IRT prior to the site confirming all eligibility criteria had been met and to whom no study medication was given. Mis-randomized patients are treated as screen failures.

Any in-eligible patient, who has been randomized and treated during the study, should be part of Randomized Set and Safety Set but excluded from FAS.

Full analysis set (FAS): The FAS will be comprised of all patients from the randomized set, to whom study treatment has been assigned. Following the intent-to-treat principle, patients will be evaluated according to the treatment assigned to at randomization.

Per-protocol set: This set includes all patients, who completed the study without a major protocol deviation.

Safety set: The safety set includes all patients, who took at least one dose of study treatment during the treatment period. Patients will be evaluated according to treatment received.

2.2.1 Subgroup of interest

There is no planned subgroup of interest.

2.3 Patient disposition, demographics and other baseline characteristics

Summary statistics will be presented for continuous demographic and baseline characteristics for each treatment group and for all patients in the randomized set. The number and percentage of patients in each category will be presented for categorical variables for each treatment group and for all patients.

2.3.1 Patient disposition

The number and percentage of patients screened will be presented. In addition, the reasons for screen failures will be provided.

The number and percentage of patients in the randomized set who enrolled, and who completed the treatment period and who discontinued the study prematurely (including the primary reason for discontinuation) will be presented at the end of each treatment period (Week 12 and Week 52), if appropriate, for each treatment group and all patients.

The number and percentage of patients who took rescue medication and hence discontinued at week 12 and week 52 will be presented. For each protocol deviation (PD), the number and percentage of patients for whom the PD applies will be tabulated.

PDs will be assigned to TP1 and TP2 based upon the starting dates. These dates are not part of the clinical database, therefore they will be provided by the clinical team in a separate file to the statistical team for analysis.

2.3.2 Patient demographic and other baseline characteristics

The following demographic and baseline variables, if collected, will be summarized:

Continuous variables:

- Age (which is derived from date/year of birth and the screening assessment date)
- Height
- Weight
- Body mass index (BMI) = (body weight in kilograms) / (height in meters)²
- For BMI, height and body weight used is the last value prior to randomization. If there is no weight recorded prior to taking of study drug, BMI will be missing.

Categorical variables:

- Age categories (<65 years, \geq 65-<75 years, 75 years and older; <45 and \geq 45 years for final analysis)
For final analysis, age groups will be redefined as <45 years, 45 years and older.
- Sex

- Race
- Ethnicity
- Child-bearing potential (for females only)
- Smoking status at baseline
- Source of patient referral

Baseline disease characteristics will also be summarized for the following variables, in two separate tables:

- History of AxPsA including time (years) since first diagnosis of AxPsA, time since first signs and symptoms, previous treatments of AxPsA and reasons for discontinuation of these treatments.
- CASPAR criteria, Patient's global assessment of disease activity and other ASAS components, SPARCC, ACR components, [REDACTED] HAQ-DI[©], FACIT-Fatigue[©], ASAS health index, Spinal pain VAS.

Unless otherwise specified, summary statistics will be presented for continuous variables for each treatment group and for all patients (total) in the randomized set. The number and percentage of patients in each category will be presented for categorical variables for each treatment group and all patients (total) in the randomized set.

Disease severity at baseline will be defined based upon BASDAI score at baseline as following:

- Group 1: 4 <= BASDAI <= 6.5
- Group 2: 6.5 < BASDAI <= 8.5
- Group 3: BASDAI > 8.5

2.3.3 Medical history

Any condition entered on the relevant medical history / current medical conditions CRF will be coded using the MedDRA dictionary. They will be summarized by system organ class (SOC) and preferred term (PT) of the MedDRA dictionary. Summaries for cardiovascular and medical history will be provided as well. Smoking history (baseline) will be summarized and listed. Analyses will be based on the randomized set.

2.4 Treatments (study treatment, rescue medication, concomitant therapies, compliance)

2.4.1 Study treatment / compliance

Study Treatment

The summaries by treatment will be performed by the actual treatment received (as follows) or treatment sequence for each treatment period.

Randomized treatment:

- AIN457 300 mg
- AIN457 150 mg
- Placebo

Treatment sequence:

- AIN457 300 mg
- AIN457 150 mg
- Placebo to AIN457 300 mg
- Placebo to AIN457 150 mg

The analysis of study treatment data will be based on the safety set. The number of active and placebo injections will be summarized by treatment group up to Week 12 and Week 52.

Duration of exposure

The duration of exposure to study treatment will also be summarized by treatment group. In addition, the number and percentage of patients with cumulative exposure levels (e.g. any exposure, ≥ 1 week, ≥ 2 weeks, ≥ 3 weeks, ≥ 4 weeks, ≥ 8 weeks, etc.) will be presented.

Duration of exposure for secukinumab groups will be defined as the time from first dose of study treatment to the time of treatment end for each treatment period. Duration of exposure for the placebo group will be defined as the time from first dose of placebo treatment to the time of treatment end in treatment period 1 and the time from first dose of active treatment to the time of treatment end in treatment period 2.

For patients who discontinue, this will be the patient's last visit in the corresponding treatment period.

Duration of exposure (years) = duration of exposure (days) / 365.25

Duration of exposure (100 patient years) = duration of exposure (years) / 100

The analyses of duration of exposure described above will be done for the entire study treatment periods.

Compliance

Compliance will be calculated based on documented study drug administrations and syringe counts and displayed by treatment group.

Compliance is expected to be 100%, unless temporary interruption is needed for safety reasons. Compliance will also be assessed by a Novartis monitor using information provided by the authorized site personnel.

2.4.2 Prior, concomitant and post therapies

Prior and concomitant therapies

Prior and concomitant medications will be summarized in separate tables by treatment group.

Prior medications are defined as treatments taken and stopped prior to first dose of study treatment. Any medication given at least once between the day of first dose of randomized study treatment and the date of the last study visit will be a concomitant medication, including those, which were started pre-baseline and continued into the period where study treatment is administered.

Medications will be presented in alphabetical order, by Anatomical Therapeutic Classification (ATC) codes and grouped by anatomical main group. Tables will show the overall number and percentage of patients receiving at least one treatment of a particular ATC code and at least one treatment in a particular anatomical main group.

Significant prior and concomitant surgeries and procedures will be summarized by primary system organ class and MedDRA preferred term.

The number and percentage of patients receiving prior and concomitant PsA therapy will be presented by randomized treatment group as well as the reasons for stopping their therapies (primary lack of efficacy, secondary lack of efficacy, lack of tolerability, other) and the total duration of exposure to PsA therapies previously.

In addition to that, summary of doses will also be performed for NSAID, MTX and corticosteroids. Comparison of median dose with ASAS recommendations will also be summarized.

Prior or concomitant medication will be identified by comparing recorded or imputed start and end dates of medication taken to the reference start date.

Rescue medication

Rescue medication is defined as medication used to control symptoms that are not adequately controlled on study treatment.

No patient will be restricted from receiving necessary rescue medications for lack of benefit or worsening of disease, if rescue with prohibited treatments occurs prior to completion of Week 52 assessments, patients can be discontinued from the study treatment (as per the CTT's discretion) but can continue with the study visit assessments until at least Week 12.

Rescue medication will be summarized similarly to concomitant medication.

2.5 Analysis of the primary objective

The primary objective is to demonstrate that efficacy of secukinumab 300 mg s.c. is superior to placebo in the achievement of ASAS 20 response at Week 12.

2.5.1 Primary endpoint

The primary efficacy endpoint is the proportion of patients with ASAS 20 response in secukinumab 300 mg s.c. and placebo at Week 12. The total spinal pain will be used for the calculation of the ASAS response.

The analysis of the primary variable will be based on the FAS.

2.5.2 Statistical hypothesis, model, and method of analysis

The statistical hypothesis for ASAS 20 being tested is that there is no difference in the proportion of patients fulfilling the ASAS 20 criteria at Week 12 in the Secukinumab 300 mg treatment group versus placebo group.

Let p_0 denotes the proportion of ASAS 20 responders at Week 12 for placebo group and p_1 denotes the proportion in secukinumab 300 mg treatment group.

In statistical terms, the following hypothesis will be tested:

$H_0: p_1 = p_0$, versus $H_{A1}: p_1 \neq p_0$

In other words,

H_0 : Secukinumab 300 mg treatment group is not different to placebo group with respect to ASAS 20 response at Week 12

The primary analyses will be conducted via logistic regression with treatment and concomitant MTX intake status as factors. The Odds ratio, 95% confidence interval (CI) and p-value will be presented comparing secukinumab 300 mg treatment group to placebo group at Week 12.

[figure not shown]
The study is said to be positive/declared as success if the lower limit of 95% CI of odds ratio is greater than 1.

Summary statistics will also be reported for each treatment group, concomitant MTX intake status and by visit. Graphical representation will also be performed.

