Response to ASAS 40 at Week 12 will be analyzed using a logistic regression model with treatment and concomitant MTX intake status as factors. The Odds ratio, 95% confidence interval (CI) and p-value will be presented comparing secukinumab to placebo.

- **BASDAI 50 at Week 12**

BASDAI 50 response is defined as at least a 50% improvement (decrease) in total BASDAI score, as compared to the Baseline total BASDAI score.

Response to BASDAI 50 at Week 12 will be analyzed using a logistic regression model with treatment and concomitant MTX intake status as factors. The Odds ratio, 95% confidence interval (CI) and p-value will be presented comparing secukinumab to placebo.

- **Spinal pain (VAS) at Week 12**

The patient's assessment of back pain will be performed using a 100 mm VAS ranging from no pain to unbearable pain.

The mean change from baseline of spinal pain at Week 12 will be analyzed by using an ANCOVA model with treatment group, visit and concomitant MTX intake status, as factors and baseline measurement in VAS as continuous covariate. The adjusted (LS) mean difference will be calculated as a point estimate together with the corresponding 95% confidence interval and p-value.

- **SPARCC enthesitis index at Week 12**

The SPARCC enthesitis index focuses on the clinical evaluation and validation of 16 defined sites.

The mean change from baseline of SPARCC enthesitis index at Week 12 will be analyzed by using an ANCOVA model with treatment group, visit and concomitant MTX intake status, as factors and baseline SPARCC index as continuous covariate. The adjusted (LS) mean difference will be calculated as a point estimate together with the corresponding 95% confidence interval and p-value.

- **Physical function index (HAQ-DI[©]) at Week 12**

Refer to Section 2.11

- **FACIT-Fatigue[®] score at Week 12**

Refer to Section 2.11

- **ASAS Health Index at Week 12**

Refer to Section 2.11

- **ACR 20 response at Week 12**

Response to ACR 20 at Week 12 will be analyzed using a logistic regression model with treatment and concomitant MTX intake status as factors. The Odds ratio, 95% confidence interval (CI) and p-value will be presented comparing secukinumab to placebo.

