2.12 Biomarkers

Not Applicable.

3 Sample size calculation

The selected criterion for the primary objective, the ASAS 20 score, is intended to be used in patients with axial skeleton involvement. Consequently, secukinumab data available from previous studies on this outcome measure, related to AS patients, can be taken into account. Compared to PsA patients, in AS patients the peripheral joints involvement is less pronounced. Thus, the ASAS 20 score for AS patients is expected to capture information entirely related to the axial skeleton involvement. Patients with PsA, who will be included in the present study, are characterized by concomitantly experiencing axial and peripheral joints disease. Thus, the ASAS 20 score is expected to also reflect the peripheral joints components.

To assume the magnitude of ASAS 20 response for PsA patients treated with secukinumab data from CAIN457F2310 (AS patients) and the CAIN457F2312 (PsA patients) have been considered.

The CAIN457F2310 study compared secukinumab to placebo in AS patients, and the ASAS 20 response rate at Week 12 was 57% for 150 mg secukinumab and 28% for placebo (300mg secukinumab was not tested). These results are a basis to extrapolate the expected results for the current study.

In a phase 3 study of Secukinumab in PsA patients, CAIN457F2312, the performance of 300 mg secukinumab is, compared to 150 mg secukinumab, numerically better in the achievement of the ACR 20 score. Assuming comparable trends in treatment response of the spine and the peripheral joints, a slightly different response between the 300 mg and the 150 mg treatment group was chosen. In addition, from data available in the literature ([Lubrano and Spadaro 2012](#)) it appears that the spinal involvement in PsA is milder compared to AS in terms of inflammation and impact on physical function, so that it can be expected that PsA patients might more easily achieve an ASAS20 score compared to AS patients. Similarly, we can assume that placebo response rates in AxPsA patients may be higher compared to AS.

[figure not shown]
For the 150 mg secukinumab treatment group a response rate of 57% is expected at Week 12.

For the 300 mg secukinumab treatment group a response rate of 60% is expected at Week 12.

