An overall type I error (2-sided) 5% will be used to control type I error. Since two secukinumab doses will be tested versus placebo in a hierarchical manner, no type-I-error adjustment is required for each comparison with respect to the primary endpoint (ASAS 20 response at Week 12). To achieve 92% power and assuming conservatively a response rate of 40% in the placebo group, at least 150 patients per group would be needed under equal allocation to show a response rate of 60% in the secukinumab 300 mg group. Using the same number of patients per group, the second test will have at least 80% power to detect a difference, if the true response rates are 57% in secukinumab 150 mg group and 40% in placebo. The above sample size calculation is based on Fisher's exact test.

To compensate for drop-outs and protocol violations, 165 patients per group (=495 total) should be recruited into this trial.

SAS® version 9.4 software was used for the calculation of sample size.

5 Appendix

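### The binary models for ASAS 20, ASAS 40 and BASDAI 50 adjust for MTX only; prespecifying baseline BASDAI as well would be valid and could add a little power

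*SAP*

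**What the plan says.** SAP 2.5.2 fixes the primary model: "The primary analyses will be conducted via logistic regression with treatment and concomitant MTX intake status as factors". Success is declared if the lower 95% confidence limit of that odds ratio exceeds 1. Section 2.6.2 uses the same model for 150 mg, and 2.7.2 uses the same two terms for ASAS 40, BASDAI 50 and ACR 20.

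The continuous endpoints are treated differently. The spinal pain model in 2.7.2, for example, has treatment, visit and MTX "as factors and baseline measurement in VAS as continuous covariate". SPARCC (2.7.2) and HAQ-DI, FACIT-Fatigue and ASAS Health Index (2.11) follow the same pattern.

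Baseline disease activity is available. Section 2.3.2 says: "Disease severity at baseline will be defined based upon BASDAI score at baseline", and forms three BASDAI groups. Section 1.1 states that randomization is not stratified.

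Baseline status does appear elsewhere. In 5.6.1 (primary analysis), baseline component scores enter the imputation model, and an additional analysis by baseline variables, including disease severity, is mentioned beside the sensitivity analyses.

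**The concern.** In a logistic model, a baseline variable that predicts response raises the power of the treatment test at the same sample size. Prespecifying it also deals with chance imbalance, which an unstratified design leaves open. The SAP uses baseline values in this way for every continuous endpoint but not for the binary ones, and gives no reason for the difference.

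What is at stake is modest: some power in the two confirmatory tests. It matters more for the 150 mg comparison, which is planned at no less than 80% power, than for the 300 mg comparison, planned at 92%.

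**Working it through.** **Inputs (SAP Section 3).** Two-sided 5% level ("An overall type I error (2-sided) 5% will be used to control type I error"). For the primary test: "To achieve 92% power and assuming conservatively a response rate of 40% in the placebo group, at least 150 patients per group would be needed". Active response rates: "For the 300 mg secukinumab treatment group a response rate of 60% is expected at Week 12" and "For the 150 mg secukinumab treatment group a response rate of 57% is expected at Week 12". The stated calculation uses Fisher's exact test without covariates.

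**Step 1: reproduce the plan's power.** Summing the binomial probabilities of all outcomes with two-sided Fisher p ≤ 0.05, at 150 per group, gives 92.9% for 60% vs 40% (plan: 92%) and 82.6% for 57% vs 40% (plan: at least 80%). The planned power therefore stands without any covariate.

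**Step 2: power of the logistic Wald test without the covariate.** Power = Φ(log OR / SE − 1.96), with SE² = 1/(n·p₁(1−p₁)) + 1/(n·p₀(1−p₀)).

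- 60% vs 40%: OR = (0.60/0.40)/(0.40/0.60) = 2.25, log OR = 0.811, SE = √(1/36 + 1/36) = 0.236, z = 3.44, power = Φ(1.48) = 93.1%.
- 57% vs 40%: OR = (0.57/0.43)/(0.40/0.60) = 1.99, log OR = 0.687, SE = √(1/36.77 + 1/36) = 0.234, z = 2.93, power = Φ(0.97) = 83.4%.

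**Step 3: add a baseline covariate.** The documents give no association between baseline BASDAI and response, so the odds ratio per SD is an assumption. The covariate X is taken as standard normal with coefficient b = log(odds ratio per SD). The intercepts a₀ and a₁ are chosen so that the average of expit(a + bX) equals the planned rate in each arm. The conditional treatment effect is a₁ − a₀. Its SE comes from inverting the information matrix for (intercept, treatment, X), and power = Φ((a₁ − a₀)/SE − 1.96).

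| Assumed OR per SD | 60% vs 40%: power (gain) | Conditional OR | 57% vs 40%: power (gain) | Conditional OR |
|---|---|---|---|---|
| 1.0 | 93.1% (0) | 2.25 | 83.4% (0) | 1.99 |
| 1.2 | 93.2% (0.2) | 2.27 | 83.7% (0.3) | 2.00 |
| 1.5 | 93.8% (0.7) | 2.32 | 84.7% (1.3) | 2.04 |
| 2.0 | 94.9% (1.8) | 2.46 | 86.7% (3.2) | 2.14 |

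Gains are in percentage points, taken from unrounded powers. As an example, at an odds ratio per SD of 2.0 the squared test statistic for 60% vs 40% rises by a factor of 1.092, so z = 3.44 × √1.092 = 3.60 and power = Φ(1.64) = 94.9%. The factor is 1.097 for 57% vs 40%. Since 150 × 0.092 ≈ 14 and 150 × 0.097 ≈ 15, the gain is worth some 14 to 15 more patients per group at the top of the range. At 1.2 the factor is 1.007, or about one patient per group.

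**Step 4: simulation check.** There were 6,000 trials per scenario, with an MTX factor in both models (assumed 40% prevalence, no effect). At an odds ratio per SD of 2.0, power went from 93.2% to 95.4% (60% vs 40%) and from 84.4% to 87.9% (57% vs 40%). With no association it did not change beyond simulation error. With 40% in both arms, and odds ratios per SD from 1.0 to 3.0, the one-sided error of the adjusted test was 2.3% to 2.8% against 2.5%. The simulation SE is √(0.025 × 0.975/6000) = 0.2 points.

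Steps 2 to 4 treat 150 patients per group as fully observed and do not model the imputation. Gains should be compared within the Wald method, not against the Fisher figures.

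**The case against.** The strongest objection is that nothing here is wrong. The model in 2.5.2 is valid, its type I error is controlled, and its power is as planned. A further covariate is a design choice. That stands: this is an improvement to consider, not a correction of an error.

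A reader might infer that the SAP itself expects baseline severity to predict response, because Section 3 says of milder spinal disease: "so that it can be expected that PsA patients might more easily achieve an ASAS20 score compared to AS patients". The sentence does not support that. It compares two diseases, and the same paragraph expects a higher placebo response as well. It says nothing about baseline BASDAI among patients within this trial.

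A reader might also call the gain free or assured. It is neither. If BASDAI is not prognostic, the gain is nil. ASAS 20 and BASDAI 50 are already defined relative to baseline (5.5.1, 5.5.3), and patients with BASDAI below 4 or spinal pain below 40 are excluded from the FAS (5.7), which narrows the covariate's range. The odds ratio also changes its meaning.

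Nor is baseline severity absent from the plan, since 5.6.1 uses it in an additional analysis. That answers part of the imbalance concern but adds nothing to the test that decides success.

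Three practical objections hold and shape the fix:

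- The documents give little support for BASDAI as the covariate for ACR 20, which rests on joint counts and other measures (5.5.7).
- The exact-regression fallback in 5.6.1 bars continuous covariates.
- Patients who did not complete an ASAS component at baseline stay in all analyses (5.7, OTH02), so a missing baseline value needs a rule.

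**Conclusion.** The point holds as a minor efficiency improvement. The text for ASAS 20 (primary and key secondary), ASAS 40 and BASDAI 50 leaves out a baseline measure that is collected and could be prespecified at almost no cost. For assumed odds ratios per SD of 1.0 to 2.0, the gain is 0 to 1.8 points for the 300 mg test and 0 to 3.2 points for the 150 mg test. The figures rest on that assumed association, a roughly normal covariate, and the SAP's response rates at 150 per group. The omission causes no bias, leaves the sample size justified, and gives no ground for calling either test underpowered.

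A related inconsistency needs correcting in any case. The GENMOD step in 5.6.1, which produces the pooled odds ratio, fits a TNF-response factor and weight and has no MTX term. Adjustment for MTX alone is therefore true of the SAP's text but not of that code. The code has no baseline disease activity either.

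**What to change.** Before the Week 12 unblinding, amend the SAP as follows:

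- In 2.5.2, 2.6.2, 2.7.2 and 5.6.1, specify logistic regression with treatment, MTX status and continuous baseline BASDAI for ASAS 20, ASAS 40 and BASDAI 50. Fit it in each imputed data set and then pool.
- Include any missing baseline BASDAI in the imputation.
- For ACR 20, adjust for a baseline measure of its own components or leave the model as it is.
- Keep treatment plus MTX as a sensitivity analysis, and keep the exact fallback without the continuous covariate.
- Make the GENMOD model statement match the text.

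The cost is SAP wording and a code revision. The code must be changed anyway, and it already carries a continuous term (weight), so a continuous covariate is workable there. No data collection or sample size changes. The price in interpretation is an odds ratio conditional on baseline BASDAI as well as MTX: for 60% vs 40%, about 2.27 to 2.46 instead of 2.25 for odds ratios per SD of 1.2 to 2.0. The fallback would estimate a slightly different quantity from the main model, and the SAP should say so.
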